6.1 General/mixed, Medical, Surgical, Other

6.2 University-affiliated, Not University-affiliated

6.3 Number of ICU beds (number)

7. Your professional focus (please choose all that apply)

Clinical, Education, Research, Management, Other (please specify)

8. Your grade (please choose all that apply)

Nurse, Trainee / non-specialist, Consultant / specialist,

University-related (Lecturer/Professor), Other (please specify)

9. Your professional intensive care experience

Less than 5 years, 5 to less than 10 years, 10 to 20 years, More than 20 years

Perceptions about provision of care for end of life / treatment limitation decisions

Please use the following 5-point scale to rate the level of importance (regarding routine/usual/standard practice) of the following domains of end-of-life patient care. Please note that the term "importance" corresponds to what the clinician considers as important for the care of ICU patients who are nearing end-of-life and have a documented poor prognosis.

1=unimportant
 2=low importance
 3=average importance
 4=high importance
 5=maximum importance

At the end of each domain, it is possible to clarify your responses and/or add other comments

10. Physical aspects of care

10.1. The patient's pain is assessed at least once daily, depending on their individual needs

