Given the above-mentioned knowledge gaps of healthcare professionals caring for critically ill patients, we propose to conduct a Europewide, descriptive survey for intensive care unit (ICU) clinicians, primarily aimed at addressing the following questions: 1) "How much of ICU everyday practice is palliative care and how is it practiced?"; and 2) "How do clinicians perceive the medico-legal framework around therapy limitations, patient autonomy and prognostication discussions with patients and families?" In addition, this survey will enable us to comparatively assess the perceived extent of ICU palliative care practice in the presence vs. absence of EOL legislation.

METHODS

Study participants and protocol approval

The target population of this descriptive, open survey will include ICU physicians and nurses working in at least 100 ICUs across at least 20 European countries. Each one of participating ICUs will be represented by one or more healthcare

professionals, and the target convenience-sample size will amount to at least 500 respondents (see also below-provided statistical analysis plan). This survey study is part of the European Union-funded Enhancing Palliative Care in ICU (EPIC) project (Proposal number: 101137221; HORIZON-HLTH-2023-DISEASE-03-01). The study protocol will be submitted for approval to the Scientific Council of Evangelismos Hospital, Athens, Greece.

Informed consent and data protection

A similar methodology has been recently described (15). According to the Helsinki declaration, participation in research requires informed consent of the participant. According to Regulation 679/2016 {or General Data Protection regulation (GDPR) of the European Parliament and of the Council, "consent" of the data subject means any freely given, specific, informed and unambiguous indication of the data subject's wishes by which he or she, by a statement or by a clear affirmative action, signifies agreement to the processing of personal data relating to him or her."

Participation in and completion of the current survey means that the participant accepts to share their knowledge on palliative care practice, EOL legislation and EOL practice in their country. The estimated time for survey completion is between 30 and 60 min.

The procedure for "*pseudonymisation*" is detailed below.

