A set of 20 consecutive random numbers (range, 10-29) will be generated using "Research Randomizer (www.randomizer.org). Each one of the aforementioned numbers will be assigned to a European country (country code) drawn according to alphabetic order from the list of participating countries. Next to the 2 digits of the country code, a one-to-three-digit number will be placed to represent each participant's temporal order of participation relative to other participants from the same country. The country-specific, temporal order of participants will be determined according to the exact time of submission of the completed study questionnaire. This will form the personal, three-to-five digit code for each study participant.

The survey database will be hosted by the CHARITE Berlin Simulation and Training Centre. Data on questionnaire domains will be stored next to the participant's personal code in Microsoft Excel format. This electronic Masterfile will be stored onto the password-protected hard disk of a personal computer. In addition, next to the participant's personal code, we will enter the following personal data 1) age; 2) gender; 3) religion; 4 and 5) country and center/city of professional activity; 6) characteristics of the participant's ICU (e.g. general, medical, surgical, etc.); 7) the participant's professional focus (e.g. clinical, research, etc.); and 8 and 9) the participant's professional grade (e.g. consultant, professor, etc.) and ICU experience (in years of work). There will be no collection/recording of participants' names or electronic mail addresses. Therefore, the Masterfile will fulfill the criterion of "*pseudonymization*."

Development and testing of the questionnaire

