We expect to determine substantial heterogeneity in the responses, primarily between northern and southern Europe and central and southern Europe, and generally between countries with high vs low palliative care service integration.

High palliative care score will be defined as presence of at least 16 positive responses (out of 24 possible positive responses) to question groups 10 through 14 of survey section 2.

Generalized estimating equations (GEE) models with robust SEs and exchangeable working correlation structure accounting for the factor center (24) will be applied to examine associations between a high palliative care score, the 9 clinician demographic variables of survey section 1 [with "country" stratified according to "northern, central or southern European region" (17,23,24)], and the EOL practice score and/or its subcomponent EOL practice variables listed in question group 24 of survey section 4. The dependent variable in this analysis will be high palliative care score, yes or no. Reference category for region will be "southern Europe" (17). The maximum number of GEE explanatory variables will be 21. Consequently, our target sample size of 500 participants is expected to result in approximately 24 observations (i.e. response data-points) per variable; this exceeds the recommended threshold of 20 observations per variable (17,23,24,25) by 20% and establishes an adequate safety margin, aimed at addressing the possibility of missing responses.

Significance will be set at two-sided $P < 0.05$. Analyses will be conducted using the latest versions of SSPS or R software.

Expected general benefits from the current study

Survey results will likely serve to refine the EPIC harmonized practice model of palliative care, further clarifying the concepts of primary versus specialist palliative care and ICU clinicians' role in the practice concept. Results from the survey on legal issues are expected to inform stakeholders involved in policy and legislation, and improve security for ICU clinicians in the respective countries and Europewide.

Expected benefits for the conduct of the EPIC trial

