15.3.1. Importance rating. 1,2,3,4,5

15.4. Do you feel empowered to document DNACPR? Yes, No, Don't know, NA

15.4.1. Importance rating. 1,2,3,4,5

15.5. Is the treating team involved in the decision for DNACPR Yes, No, Don't know, NA

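### Physicians and nurses are pooled in the yes-counts and region-level comparisons, and profession is captured only through a tick-all grade item, so a different nurse share by region could appear as a regional difference

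*Combined protocol and SAP*

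**What the plan says.** **Population.** Under Study participants and protocol approval: "The target population of this descriptive, open survey will include ICU physicians and nurses working in at least 100 ICUs". Recruitment is by convenience sample. Links go out through an anaesthesiology and intensive care society and the investigators' networks, and recipients are encouraged to pass them on (Website, survey promotion and access to the questionnaire). No quota by profession is stated.

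**How profession is recorded.** Appendix: "8. Your grade (please choose all that apply". The options are "Nurse, Trainee / non-specialist, Consultant / specialist", followed by "University-related (Lecturer/Professor), Other (please specify". The Masterfile list under Informed consent and data protection has no profession field; it records "the participant's professional grade (e.g. consultant, professor, etc.) and ICU experience (in years of work".

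**How it is used.** The Statistical analysis plan enters "the 9 clinician demographic variables of survey section 1" in a GEE model together with region, so grade is a covariate. The dependent variable is a high palliative care score, built from question groups 10 to 14. The primary outcomes are numbers of yes responses across groups 10 to 25. Country- and region-level heterogeneity and region-level comparisons are listed separately from the GEE. Neither the counts nor these comparisons are described as split or adjusted by profession.

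**The concern.** Question 8 mixes a profession with seniority levels and an academic post. Profession therefore has to be inferred, and the plan does not say how several ticks become one variable.

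This matters because some counted items depend on role. Each of groups 15 to 21 has two items on feeling empowered, one to apply and one to document, for example "Do you feel empowered to document DNACPR? Yes, No, Don't know, NA". Physicians and nurses may well answer these differently under the same law and in the same unit. With snowball recruitment, the nurse share in each country or region is whatever the networks deliver. If it differs between regions, a pooled yes-proportion differs too, even where physicians answer alike everywhere and nurses answer alike everywhere. The plan expects substantial heterogeneity between regions and intends the legal results to inform policy and legislation, so a gap caused by composition could be taken as confirmation.

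**Working it through.** **1. The plan's own figure.** 9 demographic variables + 12 EOL practice variables = 21. 500/21 = 23.8, stated as approximately 24. 24/20 = 1.20, the stated 20% margin (23.8/20 = 1.19 unrounded). The figure reproduces, and this point does not dispute it.

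**2. What question 8 can and cannot settle.** Five options give 2^5 − 1 = 31 non-empty tick patterns:

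| Pattern | Count | Reading |
|---|---|---|
| Nurse, without Trainee or Consultant | 4 | nurse |
| Nurse with Trainee and/or Consultant | 16 − 4 = 12 | nurse, if the rule is Nurse ticked = nurse |
| Trainee and/or Consultant, without Nurse | 3 × 4 = 12 | physician by default |
| University-related and/or Other only | 3 | not settled |

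These are patterns, not respondents; the documents give no frequencies. Once that rule is written down, what remains is the last row and any nurse who sits in the third row because Nurse was left unticked.

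**3. Which analyses the GEE covers.** Its outcome uses the 24 items of groups 10 to 14 (6 + 3 + 6 + 4 + 5). The empowerment items are 15.3, 15.4, 16.4, 16.5, 17.3, 17.4, 18.3, 18.4, 19.3, 19.4, 20.3, 20.4, 21.3 and 21.4: 2 × 7 = 14. None is in that outcome. They enter only the yes-counts and the region-level comparisons.

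**4. Size of a gap due to composition alone.** If the yes-rate is p_N in nurses and p_P in physicians in every region, and the nurse shares in two regions are s1 and s2, the crude gap is (s2 − s1) × (p_P − p_N). All inputs below are assumptions. The last column is the chance that an unadjusted two-proportion comparison gives P < 0.05 in the direction of the gap, by normal approximation, with 500/3 ≈ 167 respondents per region and clustering by center ignored.

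| p_N / p_P | s1 vs s2 | Region 1 | Region 2 | Gap (points) | Chance of P < 0.05 |
|---|---|---|---|---|---|
| 50% / 60% | 20% vs 40% | 58% | 56% | 2 | 6% |
| 50% / 60% | 20% vs 60% | 58% | 54% | 4 | 11% |
| 50% / 60% | 10% vs 70% | 59% | 53% | 6 | 20% |
| 50% / 70% | 20% vs 40% | 66% | 62% | 4 | 12% |
| 50% / 70% | 20% vs 60% | 66% | 58% | 8 | 32% |
| 50% / 70% | 10% vs 70% | 68% | 56% | 12 | 62% |
| 40% / 70% | 20% vs 40% | 64% | 58% | 6 | 20% |
| 40% / 70% | 20% vs 60% | 64% | 52% | 12 | 60% |
| 40% / 70% | 10% vs 70% | 67% | 49% | 18 | 92% |

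**5. How much stratifying on question 8 would recover.** Take the 8-point row (50% / 70%, 20% vs 60% nurses) and let a fraction m of nurses be read as physicians. The yes-rate in the apparent physician stratum is [(1 − s) × 0.70 + s × m × 0.50] / [(1 − s) + s × m].

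- m = 5%: 0.565/0.81 − 0.295/0.43 = 0.6975 − 0.6860 = 1.1 points
- m = 10%: 0.570/0.82 − 0.310/0.46 = 0.6951 − 0.6739 = 2.1 points
- m = 20%: 0.580/0.84 − 0.340/0.52 = 0.6905 − 0.6538 = 3.7 points

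Even imperfect stratification removes more than half of the crude 8 points in this scenario. Most of the gain therefore comes from using profession in the analysis; a cleaner item adds the rest.

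**The case against.** **Profession is recorded.** A reader might infer that no item captures it and that the two groups cannot be separated. The documents do not support that. Nurse is the first option in question 8, and tick-all lets a specialist nurse or nurse lecturer tick it alongside another role. With the rule Nurse ticked = nurse, 16 of 31 patterns flag a nurse and 12 point to a physician. Only 3 are left, and 2 of those carry the Other free text. Nothing suggests that nurses would leave Nurse unticked, and 30 clinicians took part in preliminary testing. This stands. It does not supply the missing coding rule or the missing analysis by profession.

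**The model already adjusts.** A reader might also infer that every regional result is confounded. Grade is in the GEE with region, so that model carries a proxy for profession. This stands for the high palliative care score. It does not reach groups 15 to 23 or the unadjusted comparisons.

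**NA is offered.** It is tempting to read a nurse's No on an empowerment item as scope of practice mistaken for unease with the law. But every such item offers Don't know and NA, and comfort with the legislation is asked separately, so that reading is not established. However, the outcome counts only yes, so No and NA both leave the respondent out of the count.

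**Pooling is a choice, and the items are few.** The survey describes clinicians as a whole, and by a count of the yes/no items the 14 are about 16% of 86 in groups 10 to 25. Pooled totals are legitimate as description. Comparing regions on them without regard to who answered is the weak step.

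**Conclusion.** The point holds in a limited form. Profession is captured only indirectly, there is no rule for multiple ticks, and the primary yes-counts and region-level comparisons are neither split nor adjusted by profession. A different nurse share by region could therefore show up as a regional difference, most plausibly on the 14 empowerment items that the GEE does not cover.

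The size is unknown. The 2 to 18 points rest on assumed yes-rates and nurse shares, with no true regional difference within profession, and no single value in that range should be read as an estimate. If the nurse share is similar across regions, or the two professions answer alike, there is no distortion. The documents do not show that the professions are inseparable or that the GEE region effect is unadjusted. This is a worthwhile, inexpensive improvement that removes a plausible confounder.

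**What to change.** 1. Add a single-choice profession item (Physician / Nurse / Other) and keep the remaining options of question 8 as grade. If collection has started, state in the SAP how profession is derived from question 8: Nurse ticked = nurse, whatever else is ticked; Other text reviewed; respondents who remain unclear shown as a separate category.
2. Report the yes-counts for groups 10 to 25 by profession beside the pooled totals, with denominators.
3. Stratify or adjust the region-level comparisons by profession.
4. Enter profession as its own GEE term and state how any retained grade ticks are coded.

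**Cost.** One more question, extra table columns, and smaller groups in the profession-specific tables. Counting variables as the plan does, profession as a 22nd variable gives 500/22 = 22.7 observations per variable, 13.6% above the threshold of 20. Entering the five tick-all options of question 8 as separate terms would instead give 21 − 1 + 5 = 25 terms and 500/25 = 20.0, with no margin left. That is a further reason to fix the coding in advance.

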10.1.1. Is this part of your routine practice? Yes, No, Don't know

10.1.2. Importance rating. 1,2,3,4,5

10.2. Pain relief is part of the daily ward round goals

10.2.1. Is this part of your routine practice? Yes, No, Don't know

10.2.2. Importance rating. 1,2,3,4,5

10.3. The patient's breathing/dyspnea is assessed at least once daily, depending on their individual needs

10.3.1. Is this part of your routine practice? Yes, No, Don't know

10.3.2. Importance rating. 1,2,3,4,5

10.4. Relief of dyspnea is part of the daily ward round goals

10.4.1. Is this part of your routine practice? Yes, No, Don't know

10.4.2. Importance rating. 1,2,3,4,5

10.5. The patient's other symptoms are assessed at least once daily, depending on

their individual needs.

10.5.1. Is this part of your routine practice? Yes, No, Don't know

10.5.2. Importance rating. 1,2,3,4,5

10.6. Optimizing symptom control is part of the daily ward round goals

10.6.1. Is this part of your routine practice? Yes, No, Don't know

10.6.2. Importance rating. 1,2,3,4,5

10.7. Comments (free text)

11. Psychosocial aspects of care

11.1. Various aspects of the patient's life are considered in their daily care

[For example: psychological (such as anxiety), Social, Spiritual, Existential, Financial]

11.1.1. Is this part of your routine practice? Yes, No, Don't know

11.1.2. Importance rating. 1,2,3,4,5

11.2. The patient is encouraged to participate in daily activities when able

11.2.1. Is this part of your routine practice? Yes, No, Don't know

11.2.2. Importance rating. 1,2,3,4,5

11.3. The patient's treatment preferences are considered in their daily care

11.3.1. Is this part of your routine practice? Yes, No, Don't know

11.3.2. Importance rating. 1,2,3,4,5

11.4. Comments (free text)

12. Communication and EoL care planning with the patient / family in ICU

12.1. Comprehensive and understandable information about the patient's diagnosis is provided.

12.1.1. Is this part of your routine practice? Yes, No, Don't know

12.1.2. Importance rating. 1,2,3,4,5

12.2. Comprehensive and understandable information about the patient's projected disease course is provided

12.2.1. Is this part of your routine practice? Yes, No, Don't know

12.2.2. Importance rating. 1,2,3,4,5

12.3. Comprehensive and understandable information about available treatment

options is provided**12.3.1. Is this part of your routine practice?** Yes, No, Don't know**12.3.2. Importance rating.** 1,2,3,4,5**12.4. Comprehensive and understandable information around of end-of-life care is provided****12.4.1. Is this part of your routine practice?** Yes, No, Don't know**12.4.2. Importance rating.** 1,2,3,4,5**12.5. The patient is involved in end-of-life decision-making (e.g. withholding/withdrawing life-sustaining treatments) when able.****12.5.1. Is this part of your routine practice?** Yes, No, Don't know**12.5.2. Importance rating.** 1,2,3,4,5**12.6. The family is involved in end-of-life decision-making (e.g. withholding/withdrawing life-sustaining treatments)****12.6.1. Is this part of your routine practice?** Yes, No, Don't know**12.6.2. Importance rating.** 1,2,3,4,5**12.7. Comments (free text)****13. The role of and support for the family****13.1. The family's role in care is recognized and supported****13.1.1. Is this part of your routine practice?** Yes, No, Don't know**13.1.2. Importance rating.** 1,2,3,4,5**13.2. The family's expert knowledge of the patient and advocating for patient needs are valued****13.2.1. Is this part of your routine practice?** Yes, No, Don't know**13.2.2. Importance rating.** 1,2,3,4,5**13.3. The family is being supported to prepare for the patient's death; an opportunity to say goodbye is ensured if feasible.****13.3.1. Is this part of your routine practice?** Yes, No, Don't know**13.3.2. Importance rating.** 1,2,3,4,5**13.4. Care is extended to the family after the patient's death: family members are followed up after the patient's ICU death****13.4.1. Is this part of your routine practice?** Yes, No, Don't know**13.4.2. Importance rating.** 1,2,3,4,5

13.5. Comments (free text)

14. System-level multidisciplinary support

14.1. Is there effective cooperation among members of the treating team? Yes, No, Don't know

14.1.1. Importance rating. 1,2,3,4,5

14.2. Do you think that end-of-life decisions should include an interdisciplinary team of healthcare professionals? Yes, No, Don't know

14.2.1. Importance rating. 1,2,3,4,5

14.3. Do you think that end-of-life decisions should include the patient (if feasible)?

Yes, No, Don't know

14.3.1. Importance rating. 1,2,3,4,5

14.4. Do you think that end-of-life decisions should include the family? Yes, No,

Don't know

14.4.1. Importance rating. 1,2,3,4,5

14.5. Do you think that end-of-life decisions should include others? Yes, No, Don't know

14.5.1. If yes, please specify who?

14.5.2. Importance rating. 1,2,3,4,5

14.6. Comments (free text)

Perceptions about legal framework for end of life/ treatment limitation decisions

Please use the following 5-point scale to rate the importance of the following elements of treatment limitation decisions; please note that "your country" = "the country in which you work"

- 1=unimportant
- 2=low importance
- 3=average importance
- 4=high importance
- 5=maximum importance

At the end of each domain, it is possible to clarify your responses and/or add other comments

15. Regarding Do-not-attempt cardiopulmonary resuscitation (DNACPR) orders

15.1. Are they legally allowed in your country? Yes, No, Don't know (*if no/Don't know – move on to question 16.1.*)

15.2. Do you feel comfortable with existing legislation? Yes, No, Don't know, Not applicable (NA)

15.2.1. Importance rating. 1,2,3,4,5

15.3. Do you feel empowered to apply the existing legislation? Yes, No, Don't know, NA

15.3.1. Importance rating. 1,2,3,4,5

15.4. Do you feel empowered to document DNACPR? Yes, No, Don't know, NA

15.4.1. Importance rating. 1,2,3,4,5

15.5. Is the treating team involved in the decision for DNACPR Yes, No, Don't know, NA

15.5.1. Importance rating. 1,2,3,4,5

15.6. Is the patient involved in the decision for DNACPR (if feasible)? Yes, No, Don't know, NA

15.6.1. Importance rating. 1,2,3,4,5

15.7. Is the family involved in the decision for DNACPR? Yes, No, Don't know, NA

15.7.1. Importance rating. 1,2,3,4,5**15.8. Are other persons (e.g. religious leader) involved in the decision for DNACPR?**

Yes, No, Don't know, Not applicable (NA)

15.8.1. If yes, please specify (free text)**15.8.2. Importance rating.** 1,2,3,4,5**15.9. Comments** (free text)**16. Regarding advance directives****16.1. Do they exist in your country?** Yes, No, Don't know, Not applicable (NA) (*if no/Don't know/NA – move on to question 17.1.*)**16.2. Are they legally binding in your country?** Yes, No, Don't know, NA**16.3. Do you feel comfortable with existing legislation?** Yes, No, Don't know, NA**16.3.1. Importance rating.** 1,2,3,4,5**16.4. Do you feel empowered to apply them?** Yes, No, Don't know, NA**16.4.1. Importance rating.** 1,2,3,4,5**16.5. Do you feel empowered to document them?** Yes, No, Don't know, NA**16.5.1. Importance rating.** 1,2,3,4,5**16.6. Are they regularly reviewed (e.g. every 5 years)?** Yes, No, Don't know, NA**16.6.1. Importance rating.** 1,2,3,4,5**16.7. Comments** (free text)**17. Terminal analgesia / sedation**

(the use of analgesics and sedatives in dying patients until the point of death)

17.1. Is it legally allowed in your country? Yes, No, Don't know, Not applicable (NA) (*if no/Don't know/NA – move on to question 18.1.*)**17.2. Do you feel comfortable with existing legislation?** Yes, No, Don't know, Not applicable (NA)**17.2.1. Importance rating.** 1,2,3,4,5**17.3. Do you feel empowered to apply it?** Yes, No, Don't know, NA**17.3.1. Importance rating.** 1,2,3,4,5**17.4. Do you feel empowered to document it?** Yes, No, Don't know, NA

